4.2.3.9 Duration of iBOR

The duration of iBOR is defined as the length of time from the date when iBOR is first documented until the date of death or the date when a change in disease state using iRECIST is objectively documented, whichever is earlier. Patients who remain alive and do not change from iBOR in disease state are censored on the date of their last tumor assessment. Patients who start a new therapy and do not change from iBOR in disease state are censored at the last tumor assessment prior to initiating the subsequent anticancer therapy. Duration of iBOR is only evaluated in patients with a documented disease state.

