In patients who have initial evidence of radiological PD, it is at the discretion of the treating physician whether to continue a patient on study treatment until repeat imaging is obtained. This clinical judgment decision should be based on the patient's overall clinical condition, including performance status, clinical symptoms, and laboratory data.

iRECIST criteria include the above RECIST 1.1 derived criteria (see Table 11 and Table 12 below) with the proviso that the increase in tumor burden must be shown to increase, but in the case of iUSD, iUPR or iCR, the assessment time bar is reset.

For target lesions, iCR, iPR and iSD can all be assigned after iUPD has been documented as long as iCPD has not been confirmed. Progression is confirmed in the target lesion category if the next imaging assessment after iUPD (4-8 weeks later) confirms an increase in the sum of target lesions dimensions of greater than 5 mm. However, iCPD is not met if the imaging assessment after iUPD is followed by CR, PR or SD (compared to baseline as defined in RECIST 1.1). The status is reset and assessment continues. Please note this is different from RECIST 1.1

Thus iUPD can be assigned on multiple occasions, as long as iCPD is not declared.

Table 11 Comparison of RECIST 1.1, iRECIST and irRECIST

	RECIST 1.1	iRECIST	irRECIST
Definitions of disease: numbers, sites and target or non	Measurable are diameters greater than 10 mm (15 for nodes maximum of 5 (2 per organ))	No change from RECIST 1.1	No change from RECIST 1.1
CR, PR or SD	Cannot have met criteria for progression	Can have had iUPD (more than once) but not iCPD before iCR, iPR or iSD	Use of terminology based around RECIST 1.1
Confirmation of CR or PR	Only in non-randomized studies	As per RECIST 1.1	As per RECIST 1.1
Confirmation of SD	Not required	As per RECIST 1.1	As per RECIST 1.1
New lesions	Progression: recorded but not measured	iUPD but only becomes iCPD if on the next scan there are new lesions or the size increases by greater than 5 mm	Unclear
Confirmation of progression	Not required	Required	Required
Consideration of clinical status	Not required	Clinical stability considered at iUPD to decide treatment continuation	As iRECIST without terminology considering unconfirmed findings

Table 12 Trajectory of progression in iRECIST

Target Lesions: iCR, Non-target: iCR, no new lesions	iCR	iCR
Target lesions: iCR, Non-target: non iCR/non iUPD, no new lesions	iPR	iPR

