4.2.3.7 Overall response assessed through iRECIST

The categorization using iRECIST is equivalent with the categorization using RECIST 1.1 until PD. Once PD is obtained, RECIST 1.1 will stop whereas iRECIST will continue to characterize disease state also in cycles after PD.

A patient with a best overall response of either iCP or iPR is defined as a patient with an overall response according to iRECIST. A tumor measurement categorized as iCP or iPR needs a confirmed response of either iCP or iPR at least 4 weeks after the initial response assessment to be classified as best overall response iCP or iPR.

Examples of patients with an overall response are patients with the following outcome of iRECIST at cycle 3 (week 9) and subsequent every 3rd cycles:

- iSD, iSD, iPR, iPR, iSD; iPD (overall response as iPR in cycle 9 and confirmed in cycle 12)
- iSD, iSD, iSD, iCR, iCR (overall response as iCR in cycle 4)
- iSD, PD(iUPD), iPR, iPR, iSD (overall response as iPR as assessed by iRECIST in cycle 9 and confirmed in cycle 12)

Example of patients with no overall response:

- iSD, iSD, iSD, iSD, iSD, iSD, iSD, iSD, iSD
- iSD, (iUPD), iSD, iSD, iCPD
- iSD, iSD, iPR, iSD, iSD, iUPD (iPR in cycle 9 is not confirmed)
- iSD, (iUPD), iSD,

The overall response rate (ORR) using iRECIST is defined as the percentages of patients that are classified as overall responders assessed through iRECIST as described above.

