4.2.3.8 Immune Best Overall Response (iBOR)

The immune best overall response (iBOR) is the best timepoint response recorded from the start of the study treatment until the last assessment of tumor response recorded during study period or the start of post treatment cancer therapy (whichever is sooner), taking into account any requirement for confirmation. iUPD will not override a subsequent best overall response of iSD, iPR, or iCR, meaning that iPR or iSD can be assigned (timepoint response or iBOR) even if new lesions have not regressed, or if unequivocal progression (non-target lesions) remains unchanged, providing that the criteria for iCPD are not met. Table 3 gives scenarios for assignment of iBOR (Seymour (2017)).

Table 3 Scenarios of assignments of best overall response using iRECIST

	Timepoint response 1	Timepoint response 2	Timepoint response 3	Timepoint response 4	Timepoint response 5	iBOR
Example 1	iCR	iCR, iPR, iUPD, or NE	iCR, iPR, iUPD, or NE	iUPD	iCPD	iCR
Example 2	iUPD	iPR, iSD, or NE	iCR	iCR, iUPD, or NE	iCR, iPR, iSD, iUPD, iCPD, or NE	iCR
Example 3	iUPD	iPR	iPR, iSD, iUPD, or NE	iPR, iSD, iUPD, NE, or iCPD	iPR, iSD, iUPD, NE, or iCPD	iPR
Example 4	iUPD	iSD or NE	iPR	iPR, iSD, iUPD, or NE	iPR, iSD, iUPD, iCPD, or NE	iPR
Example 5	iUPD	iSD	iSD, iUPD, or NE	iSD, iUPD, iCPD, or NE	iSD, iUPD, iCPD, or NE	iSD
Example 6	iUPD	iCPD	Any	Any	Any	iCPD
Example 7	iUPD	iUPD (no iCPD)	iCPD	Any	Any	iCPD
Example 8	iUPD	NE	NE	NE	NE	iUPD

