4.2.3.11 Immune Clinical Benefit Rate (iCBR)

The iCBR is defined as the percentage of patients with the best measurement of response categorized as iCR, iPR or iSD. Note that iSD requires no confirmation as is required for the immune best overall response of either iCR or iPR. The first tumor assessment is planned to occur 9 weeks after first dose and therefore, iSD documented at the first assessment would typically qualify as iSD. However, an iSD with actual assessment time less than 6 weeks after first dose will not be qualified as iSD. Patients with no post-baseline tumor assessments are considered to have achieved no clinical benefit according to iRECIST.

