4.2.3.13 Duration of immune response

Duration of immune response is defined as the length of time from the first date of confirmed iCR/iPR to the date of death or the date of first documented tumor progression (iUPD) provided that iCPD is confirmed at the next assessment, whichever is earlier, using iRECIST. Patients who remain alive and do not progress are censored on the date of their last tumor assessment. Patients who start a new therapy without a prior iUPD are censored at the last tumor assessment prior to initiating the subsequent anticancer therapy. Response duration is only evaluated in patients with an overall immune response of iCR or iPR.

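### Duration of iBOR ends at any change of iRECIST category, so drift without progression and an unconfirmed progression that resets count as events (exploratory endpoint only)

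*SAP*

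**What the plan says.** SAP 4.2.3.9 starts the clock when iBOR is first documented and runs it "until the date of death or the date when a change in disease state using iRECIST is objectively documented, whichever is earlier". The censoring rule is the mirror image: "Patients who remain alive and do not change from iBOR in disease state are censored on the date of their last tumor assessment". A second rule applies the same condition to patients who start new therapy, censoring them at the last assessment before it. On who is included, the section says: "Duration of iBOR is only evaluated in patients with a documented disease state".

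Three other places bear on how this works.

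- **Resets.** Protocol 9.1.4 says: "However, iCPD is not met if the imaging assessment after iUPD is followed by CR, PR or SD". The status then resets and assessment continues.
- **Confirmation.** SAP 4.2.3.8 assigns iBOR "taking into account any requirement for confirmation". SAP 4.2.3.11 adds: "Note that iSD requires no confirmation as is required for the immune best overall response of either iCR or iPR". SAP 4.2.3.7 lists, as an example of a patient without overall response, "iSD, iSD, iPR, iSD, iSD, iUPD (iPR in cycle 9 is not confirmed".
- **The neighbouring endpoint.** SAP 4.2.3.13 ends duration of immune response at death or at "the date of first documented tumor progression (iUPD) provided that iCPD is confirmed at the next assessment".

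SAP 5.3 analyses the time-to-event endpoints of Section 4.2.3 by Kaplan-Meier. SAP 5.6.3 treats the exploratory endpoints descriptively. The protocol lists duration of iBOR but does not define it.

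**The concern.** A reader who meets a Kaplan-Meier median titled duration of iBOR will probably take it as how long the best result held before the disease progressed. Under the rule as written it is the time until the category label changes for any reason. The curve would mix progression, movement of the tumor sum across the partial-response threshold, flares that resolve and possibly improvement.

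The treatment of flares is also uneven. Under SAP 4.2.3.8 an iUPD before the best response does not stand in its way. Under 4.2.3.9 an iUPD after the best response ends its duration at once, even if the next scan resets it. Protocol 9.1.4 brought in iRECIST because an early increase in tumor burden may be followed by response. What is at stake is the interpretation of one exploratory summary.

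**Working it through.** The plan states no figure for this endpoint, so there is nothing to reproduce. The check applies the rule to the SAP's own example sequences.

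**Inputs**
- Sequences: SAP 4.2.3.7.
- Scan times: weeks 9, 18, 27, 36, 45, 54 (SAP 4.2.3, first scan at week 9 and then after every third cycle).
- Rule as written: duration = week of first category other than iBOR − week iBOR first documented.
- Comparison: duration = week of confirmed progression − week iBOR first documented, dated at the iUPD when iCPD follows at the next assessment, as in SAP 4.2.3.13.

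**A. Drift: iSD, iSD, iPR, iPR, iSD, then progression.** iBOR is iPR from week 27, confirmed at week 36.
- As written, the iSD at week 45 is the event: 45 − 27 = 18 weeks.
- With confirmed progression, the event is at week 54: 54 − 27 = 27 weeks. The listing stops at progression, so confirmation at the next scan is assumed.

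**B. Flare that resets: iSD, iUPD, iSD, iSD, iCPD.** iBOR is iSD from week 9.
- As written, the iUPD at week 18 is the event: 18 − 9 = 9 weeks.
- With confirmed progression, the event is at week 45: 45 − 9 = 36 weeks. The listing shows no iUPD directly before the iCPD. An unlisted one between weeks 36 and 45 would put the figure between 36 − 9 = 27 and 36 weeks.

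**C. Unconfirmed iPR: iSD, iSD, iPR, iSD, iSD, iUPD.** By the confirmation text, iBOR is iSD from week 9.
- As written, the iPR at week 27 is the event: 27 − 9 = 18 weeks.
- With confirmed progression, the event is at week 54: 54 − 9 = 45 weeks, with confirmation at the next scan assumed.
- Other reading: Table 3, Examples 3 and 4, gives iBOR = iPR where one iPR may be followed by iSD, iUPD or NE. The clock then starts at week 27. The rule as written ends it at the iSD in week 36 (36 − 27 = 9 weeks), against 54 − 27 = 27 weeks. A category change still ends it, but that change is not an improvement.

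**D. Response after a flare: iSD, iUPD, iPR, iPR, iSD.** iBOR is iPR from week 27, and the last scan is at week 45. Both rules give 45 − 27 = 18 weeks, but as an event under the rule as written and as a censored time under the comparison.

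**Population.** A documented disease state includes progression. Table 3 gives iBOR = iCPD in Examples 6 and 7 and iUPD in Example 8. For these patients the present rule measures time spent in a progression category.

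**The case against.** The strongest reply is that the SAP may mean what it says. Duration of iBOR, time to iCPD and duration of immune response are listed as separate endpoints. Confirmed progression already ends the last of these, and time to iCPD has its own definition. Read with its censoring sentence, 4.2.3.9 is a coherent definition of time in the best category.

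Much of this stands. A reader might infer that 4.2.3.9 and 4.2.3.13 contradict each other. They do not: they define two differently named endpoints, and the difference is one of approach. A reader might also say that the SAP treats drift or improvement as the end of benefit. The SAP does not use that term here; it deals with benefit in 4.2.3.11, where iCR, iPR and iSD all count. Nor is Protocol 9.1.4 breached, since the reset governs whether iCPD is declared, not when a duration ends. The improvement case cannot be stated without its condition, because Table 3 can be read against it.

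What does not stand is the idea that the intention is clear. Nothing in either document calls the endpoint time in the best category, and nothing narrows the event. Cases A and B hold on either reading of Table 3.

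**Conclusion.** The point holds for the event definition. As written, a move from iPR to iSD without progression and an iUPD that resets are both Kaplan-Meier events. An improvement from iSD to iPR is an event only if iBOR stays iSD after an unconfirmed iPR.

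Relative to confirmed progression, the durations are shorter by 27 − 18 = 9 weeks (drift), 36 − 9 = 27 weeks (flare; at least 27 − 9 = 18 if an unlisted iUPD preceded the iCPD) and, conditionally, 45 − 18 = 27 weeks (unconfirmed iPR). These are single illustrative patients on the planned scan schedule. The documents do not say how often such sequences will occur, so the shift in the Kaplan-Meier median cannot be estimated.

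It would be wrong to infer that the trial's main conclusions are affected. SAP 5.6 confines formal testing to ORR by RECIST 1.1 in the three main cohorts, and the interim rules in SAP 5.4.3 do not use duration of iBOR. This is a minor point, worth making because the repair is cheap.

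**What to change.** Four linked changes in SAP 4.2.3.8 and 4.2.3.9. The first is not enough alone: without the second, a patient whose iBOR is iCPD could have an end date before the start date; without the third, a living patient who moves from iPR to iSD would have neither an event nor a censoring rule.

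1. End the duration at death or at the first iUPD after iBOR is documented for which iCPD is confirmed, whichever is earlier, using the confirmation wording of 4.2.3.13. State that changes among iCR, iPR and iSD, and an iUPD that resets, do not end it.
2. Limit the endpoint to patients whose iBOR is iCR, iPR or iSD.
3. Reword both censoring rules so that they apply to patients without death or confirmed progression. Censor at the last tumor assessment, or at the last one before new anticancer therapy.
4. Align Table 3 with the confirmation rule.

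The cost is a few sentences and no new data. The downside is overlap: for responders the end event then matches duration of immune response, although start dates can still differ (for example when iCR follows iPR), so the added information comes mainly from iSD patients. Also, Protocol 9.1.5 does not require repeat imaging in clinically unstable patients. Some progressions will stay unconfirmed and be censored unless death follows, as already happens under 4.2.3.13.

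If time in the best category is what the sponsor wants, the alternative is to keep the event rule, retitle the endpoint and say so in the definition.

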5.3 General Principles for Presenting Study Data

All statistical analyses will be performed at SDS using SAS® (Version 9.3 or higher, SAS Institute Inc., Cary, NC, USA). All statistical analyses will be performed after this SAP is finalised and approved and the study database is locked.

Continuous data will be summarized using descriptive statistics where the following parameters will be reported:

- Number of observations (n),
- Mean,
- Median,
- Standard deviation (SD),

- Range (Min, Max)

Categorical data will be presented as the number and percentage of patients.

Time to event endpoints defined in Section 4.2.3 (e.g. duration of response, OS and time to iCPD) will be analysed using Kaplan-Meier methods taking censoring into account. The Kaplan-Meier plot and corresponding estimate of the median value with 95% confidence interval will be reported.

All tests will be one-sided and performed at the 5% significance level. When reporting the results of significance tests, p-values will be reported together with 2-sided 90% confidence intervals.

Throughout the report, the number of decimal places given for the summary statistics; mean, STD, confidence interval and median values will exceed that of the source data by one. Minimum and maximum will have the same number of decimal places as the source data. For relative frequencies, integer with one decimal and %-sign will be presented and for p-values four (three) decimals will be reported.

Percentages will be based on number of patients with data at a certain time point with the exception of presentations of medical history, medications and AEs where the percentages will be based on the number of patients in the study population.

In general, all data will be listed, sorted by phase of study, cohort and patient, and when appropriate by cycle within patient. All summary tables will be structured with a column for cohort and will be annotated with the total population size relevant to that table/cohort, including any missing observations. Summary tables will include summaries for visits for Cycle 1 (Screening, Day 1 pre dose, Day 1 post dose, Day 8 pre dose, Day 8 post dose and Day 22 End of Cycle 1 as appropriate) whereas subsequent cycles will be summarized with summary statistics for the minimum and maximum observed value during the subsequent cycles.

The two phases of the study will be summarized separately. In addition, cohorts from phase 1 and phase 2 may be combined and summarized if appropriate.

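### Duration of iBOR is evaluated in patients whose best response is progression, so its Kaplan-Meier estimate mixes time in response or stable disease with time after progression

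*SAP*

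**What the plan says.** SAP 4.2.3.9 starts the interval when iBOR is first documented and runs it "until the date of death or the date when a change in disease state using iRECIST is objectively documented, whichever is earlier". On censoring it says: "Patients who remain alive and do not change from iBOR in disease state are censored on the date of their last tumor assessment". A patient who begins another cancer treatment while still in the iBOR state is censored at the last scan before that treatment. The section closes with the inclusion rule: "Duration of iBOR is only evaluated in patients with a documented disease state".

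Table 3 in SAP 4.2.3.8 shows which values iBOR can take. Two rows matter here: "Example 6 iUPD iCPD Any Any Any iCPD" and "Example 8 iUPD NE NE NE NE iUPD". The last entry in each row is the assigned iBOR. Example 7 also ends in iCPD.

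SAP 5.3 covers the time-to-event endpoints of 4.2.3: "The Kaplan-Meier plot and corresponding estimate of the median value with 95% confidence interval will be reported". SAP 5.6.3 applies 5.3 to the exploratory endpoints in the Efficacy Evaluable Population. Tables carry a column for cohort, and SAP 5.4.5 and 5.6.4 plan no subgroup analysis.

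**The concern.** SAP 2.2.3 places duration of iBOR among the measures of effect on tumor response. For a patient whose iBOR is iCR or iPR, a long interval is a lasting response. For a patient whose iBOR is iCPD, the same variable measures time lived after confirmed progression. One curve over both does not describe how long benefit lasts, because it also depends on when patients with progression die.

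What is at stake is the reading of one descriptive endpoint, not a decision rule. It matters most in the dose-escalation phase. There SAP 4.2.1.3 lists only iBOR, duration of iBOR and time to iCPD, so no other iRECIST duration is available to set beside it.

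**Working it through.** The plan states no expected value or precision for this endpoint, so there is no figure to reproduce. The check is to follow the rule through.

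**1. Who enters.** The rule asks only for a documented disease state. SAP 4.2.3.7 uses that term for states after progression: "iRECIST will continue to characterize disease state also in cycles after PD". With Table 3 allowing iBOR of iCPD or iUPD, such patients are in. The rule's evident effect is to leave out patients with no evaluable state.

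**2. What is measured, by iBOR category.**

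| iBOR | Clock starts at | Clock usually stops at |
|---|---|---|
| iCR or iPR | first scan in that state | loss of that state, or death |
| iSD | first scan in that state | loss of that state, or death |
| iCPD | scan confirming progression | death, or censoring at the last scan |
| iUPD | scan first showing progression | death, or censoring at the last scan |

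In the last two rows, improvement before confirmation would have given a better iBOR, so the interval rarely ends in a change of state. Table 3 does allow any state after iCPD, so a later scan could still end it.

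**3. What follow-up exists after progression.** Protocol 9.1.3 ends scheduled scanning at site-assessed progression. Protocol 9.1.5, Table 13, requires no further imaging once progression is confirmed, and leaves repeat imaging of clinically unstable patients to the physician. Exceptions exist, such as continued treatment agreed with the sponsor. Survival is still followed by telephone every 3 months (Protocol 6.3.3). So after the iCPD scan there is usually no later scan, but there may be a date of death.

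**4. Effect on the Kaplan-Meier estimate.** A living iCPD patient with no later scan has last assessment = iCPD scan, hence duration 0, censored. Such a record leaves the risk set at once. The same holds for an iCPD patient who starts new therapy. An iCPD patient who dies without recorded new therapy contributes an event at (date of death − date of iCPD scan). Among progressors without later scans, those still at risk after time zero are therefore exactly those who die. These deaths enter the same curve as losses of response.

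**5. Direction only, with assumed inputs.** Take exponential durations with no censoring. Shares are 20% iCR/iPR, 20% iSD and 60% progressors. Medians are 12 months for iCR/iPR, 4 for iSD, and m for progression to death. None of these values is in the documents. The pooled median t solves

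0.20·2^(−t/12) + 0.20·2^(−t/4) + 0.60·2^(−t/m) = 0.5

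- m = 3 gives t = 4.0 months (0.159 + 0.100 + 0.238 ≈ 0.50).
- m = 9 gives t = 8.0 months (0.126 + 0.050 + 0.324 = 0.50).
- If every progressor were censored at time zero, only iCR/iPR/iSD would remain, in equal shares, and t = 6.6 months.

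Response and iSD durations are the same in all three lines. This shows that the estimate can move in either direction for reasons unrelated to response. It is not an estimate of the effect here, because the plan's censoring rules lie somewhere between these cases.

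**6. Comparison within the SAP.** SAP 4.2.3.5 limits duration of response to CR or PR, and 4.2.3.13 limits duration of immune response to iCR or iPR. Of the three duration definitions, only 4.2.3.9 admits patients whose best state is progression.

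**The case against.** The strongest reply is that nothing turns on this. The only formal analysis is ORR by RECIST 1.1 (SAP 5.6). Duration of iBOR is descriptive, and the expansion phase already has a responder-only iRECIST duration in 4.2.3.13. That stands, and it limits the weight of the point. It does not cover dose escalation, where 4.2.1.3 lists no such endpoint.

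A second reply is that pooling is inferred. The SAP nowhere says that all iBOR categories share one curve, and the mock-up tables and figures are separate documents that might split them. That is fair. But the SAP specifies no split, and a programmer following it would produce one estimate per cohort.

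A reader might also go further and infer that progressors dominate the median. The design response rates of 5% to 30% leave 70% to 95% of patients as non-responders; even at the good-drug rates, expected responders are 27 × 0.20 = 5.4, 26 × 0.25 = 6.5 and 25 × 0.30 = 7.5. The documents do not support that inference. The non-responder share includes iSD, which is not time after progression, and no split between iSD and progression is given. The rates are for RECIST 1.1 rather than iRECIST, and the good-drug rates are lower limits. Progressors censored at time zero add almost nothing to the curve.

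**Conclusion.** The inclusion rule is wrong for what the endpoint is meant to describe. As written, and with no split specified, each cohort's estimate combines durations of iCR/iPR and iSD with intervals that begin at progression. It can shift with deaths after progression without any change in response. The size of the shift cannot be derived from the documents: it depends on how many progressors die without recorded new therapy, how soon they die, and how many have later scans.

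The conclusion assumes that 4.2.3.9 is applied literally and that no unseen table template separates the categories. The point is minor. The endpoint is exploratory, and the durations in 4.2.3.5 and 4.2.3.13 are unaffected. It would be wrong to infer that the SAP lacks a clean iRECIST duration of response altogether; it lacks one only in the dose-escalation list.

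**What to change.** Replace the last sentence of SAP 4.2.3.9 with wording such as: *Duration of iBOR will be evaluated only in patients whose iBOR is iCR, iPR or iSD; patients with an iBOR of iUPD or iCPD are not included. Results will be given separately for iCR/iPR and for iSD.*

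The cost is one sentence and matching table shells, with no new data. Each estimate will rest on fewer patients. In the expansion phase the iCR/iPR part will partly overlap duration of immune response in 4.2.3.13, differing mainly in the event that ends the interval.
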